4.10.19 Ethics Statement

Ethical approval will be sought from the necessary institutional review boards, JREC and MRCZ. All study participants will give written informed consent. Permission for storage and future use of biological specimens, external shipping of specimens including genetic testing of blood samples will also be sought. This observational study involves minimal risks to both the mother and the baby hence one parental consent is sufficient. However, in case of death of the mother re-consenting will be done from either the father or any family member who shall have legal responsibility for the care and custody of the baby. In case of a child death, the mother will cease to continue participating in the study.

Permission has already been obtained from Harare City Health. The sensitivity of HIV infection and sexuality means that the mother's emotional response is a potential risk. Anxiety associated with sample testing and waiting for the results for HIV exposed children may also be experienced. Nevertheless the study will minimize such risks by providing the necessary education and counselling through the research nurses and where necessary, referring them to the appropriate clinics. Health education and counselling on pregnancy, delivery and childcare will be given to mothers on a continuous basis at every visit. The study will offer consultation and basic treatment to both the mother and child. Whenever necessary referrals will made through the clinic.

Each sub-study will apply for their respective ethical approvals to all the relevant ethical boards before they can access the data and/or specimens. However, some sub-studies may require separate consent forms should they entail collection of additional data from study participants. Those that rely on specimens and data collected through main study will need no additional informed consent.

4.10.20 Adverse Event Monitoring and Reporting

All Severe Adverse Events (SAEs): prolonged hospitalisation, life threatening, congenital birth defects and significant disabilities including deaths will be reported to MRCZ and sponsor within 24 hours of first becoming aware of it. Regular monitoring visits to the investigative sites will be conducted by UZ-CHS Research Support Centre (RSC) monitors in accordance with a site monitoring

plan which will be finalised by RSC before screening begins. The frequency and duration of visits will be sufficient to allow monitoring of:

- 1. Compliance with the informed consent process and documentation
- 2. Adequacy of maintenance of participant files
- 3. Accuracy of transfer of data from participant trial files into the CRFs
- 4. Compliance with the current version of the protocol
- 5. Ongoing assumption by the PI of primary responsibility for conduct of the study
- 6. Storage and handling of biological specimens.
- 7. Compliance with all regulatory requirements

4.10.21 Data Management Plan

Study data will be collected and managed using Research Electronic Data Capture(REDCap) tool hosted at the UZ RSC. Quality assurance on the accuracy of data entry will employed including independent double entries. Data analysis will be carried out using statistical packages such as; Stata version 13 and Statistical Package for the Social Sciences SPSS. Categorical data will be compared using chi squared test. Continuous variables will be compared between groups using analysis of variance (parametric) and sum rank (non-parametric) tests. Continuous variables will be correlated using regression models.

4.10.22 Data analysis

The data were collected and analyzed using SPSS (version17.0, Chicago, IL). Viral load values were log₁₀ transformed. The Student's t-test was used to compare means. Regression analysis was used to investigate the associations Tests of statistical significance included the 95% confidence interval of unadjusted relative risks, two-sided p values based on Chi-square and Fisher's exact tests. Sequences were assembled using the Vector NTI Advance 10 program. Alignment was attained using Gene Doc, BioEdit, and Clustal X2 sequence alignment programs including manual editing to ensure that deletions or insertions did not alter the reading frame.

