	different comorbidities in isolation or combinations among mothers and infants.
	uniterent comorbiances in isolation of comornations among motiers and infants.
	-
	4. To correlate maternal plasma viral load, soluble biomarkers immune activation profiles and diseases
	4. To correlate maternal plasma viral load, soluble biomarkers immune activation profiles and diseases progression and duration of HAART treatment among HIV+ mothers
	 To correlate maternal plasma viral load, soluble biomarkers immune activation profiles and diseases progression and duration of HAART treatment among HIV+ mothers To determine any association of different HAART regimens and pregnancy outcome, infant growth and
Primary	 To correlate maternal plasma viral load, soluble biomarkers immune activation profiles and diseases progression and duration of HAART treatment among HIV+ mothers To determine any association of different HAART regimens and pregnancy outcome, infant growth and immune/neuro-development among HIV+ mothers
Primary end points	 To correlate maternal plasma viral load, soluble biomarkers immune activation profiles and diseases progression and duration of HAART treatment among HIV+ mothers To determine any association of different HAART regimens and pregnancy outcome, infant growth and immune/neuro-development among HIV+ mothers Prevalence, trends and incidence of comorbidities among HIV+ and HIV- mothers
•	 To correlate maternal plasma viral load, soluble biomarkers immune activation profiles and diseases progression and duration of HAART treatment among HIV+ mothers To determine any association of different HAART regimens and pregnancy outcome, infant growth and immune/neuro-development among HIV+ mothers Prevalence, trends and incidence of comorbidities among HIV+ and HIV- mothers Pregnancy outcomes for HIV-/+ mothers with different comorbidities with or without different HAART
•	 To correlate maternal plasma viral load, soluble biomarkers immune activation profiles and diseases progression and duration of HAART treatment among HIV+ mothers To determine any association of different HAART regimens and pregnancy outcome, infant growth and immune/neuro-development among HIV+ mothers Prevalence, trends and incidence of comorbidities among HIV+ and HIV- mothers Pregnancy outcomes for HIV-/+ mothers with different comorbidities with or without different HAART regimens

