
1.11 Maternal Psycho-Social Factors

Undiagnosed maternal HIV infection prior to conception, unplanned pregnancies, delays in accessing antenatal care, non-disclosure of the pregnant women's HIV status to her partner and low levels of education are some of the most significant maternal risk factors associated with vertical transmission and or infant death ²¹⁸⁻²²⁰. Directly disclosing a positive HIV sero-status to family members can have psychological and physiological health benefits ²²¹. Hence disclosure of HIV sero-status by women to their sexual partners is critical for the success of the PMTCT programme as an integrated service in antenatal care. Pregnant HIV-negative women and their unborn babies remained at risk of HIV infection owing to the resistance of their partners to go for HIV testing ²²². Poverty, lack of support, HIV, witchcraft and child illness have been identified as causes of worry in the perinatal period ^{223;224}. Adverse maternal health and feotal outcomes have been shown to be more prevalent in socioeconomically-disadvantaged women²²⁵. Depression and its impact on maternal and child health has important implications with depressed mood being associated with alcohol use, less breastfeeding and low birth weight ^{226;227}. Smoking increases the risk of morbidity and mortality and is particularly harmful to pregnant mothers. Chronic maternal marijuana use has been associated with early sex in offspring ²²⁸.Studies have shown that alcohol use and HIV sero-status of partner predict high-risk sexual behaviour among patients receiving antiretroviral therapy ^{229;230}. Alcohol-exposed pregnancy is a significant public health problem as alcohol consumption is associated with feotal abnormalities and long-term cognitive problems depending on the amount consumed, drinking pattern, and time of gestation. Feotal alcohol exposure is a leading cause of developmental disabilities and mental retardation ²³¹. Prenatal cocaine exposure has been linked to child behaviour problems²²⁸. Screening for alcohol use disorders and substance uses are important to reduce alcohol consumption during pregnancy and associated problems in infants. Intimate partner violence defined as actual or threatened physical, sexual, psychological and emotional abuse by current or former partners is a global public health concern ^{232;233}. Hence there is need to manage health related stress. There is significant current interest in the degree to which prenatal exposures to stress influence infant outcomes. Such maternal psycho-socio and demographic factors also play a role in infant mortality and necessary interventions for common perinatal mental disorders may be required.

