
There is paucity of information regarding the impact of environmental factors related to being born in an HIV-affected household especially of low social economic status and how this impacts on child care practices. Limited data exists which explores the possible associations between the mothers' psychosocial and economic wellbeing during the prenatal and postnatal period and increased

psychosocial and economic wellbeing during the prenatal and postnatal period and increased morbidity and mortality among HEU infants in the first year of life. It is against this background that in addition to investigating the abnormal immunity of HEU and the associated maternal genetic and environmental factors. For the holistic and integrative research, numerous other related sub-studies addressing other coinfections, NCD and maternal psycho social aspects will be developed for a full assessment of the common comorbidities. Each of these comorbidities in isolation and/or combination may be assigned characteristic immune biomarkers assayed from one blood plasma sample and such a development may lead to powerful tool to optimize and individualize treatment and care. Other sub studies linked to this study also seeking to determine the maternal psychological wellbeing such as stress and depression including other important co-infections such as Tb, herpes simplex virus (HSV), human papilloma virus (HPV), bacterial vaginosis, (BV) infections gut and vaginal microbiomes associated with high morbidity and mortality among HEU infants will be developed. In general, research questions will fall into seven thematic areas namely, co-infections, non-communicable diseases, nutrition, immunogenetics, pharmacokinetics/dynamics/genomics, psychosocial and child growth and development. See **Appendix 6.1**.

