3.1 Main Objective

This study aims to establish a birth cohort to investigate the role of HIV and comorbidities on vertical HIV transmission, immune development and disease progression in children 0-2 years, HEU, HEI and HUU as the control group.

Objectives

A. All Mothers Regardless of HIV Status

- To determine the prevalence and incidence of coinfections (intestinal parasitic infections, HBV, HCV, CMV) malnutrition and non-communicable diseases (NCDs) (gestational diabetes mellitus, hypertensive disorders and CVD) risk factors over 24 months and relate all these comorbidities to:
 - a. Pregnancy outcome, infant growth, development, morbidity and mortality
 - b. Biomarkers of inflammation and immune activations

Infants

- 2. To determine vertically transmitted infections and incidence non-communicable diseases among infants.
- 3. To determine clinical and immunological profiles of HEI, HEU and HUU infants.

B. HIV+ Mothers: Chronic HIV infections

- 1. To determine vertical transmission rates of mothers with acute and chronic HIV infection on option B+
- 2. Determine any association(s) between different option B+ drug regimens, adverse pregnancy outcome, viral load suppression and CD4/CD8 counts on mothers and their infants

C. HIV+ Mothers; Acute HIV infections,

- 1. To determine the incidence of HIV in the postpartum period over the 2 years
- 2. To determine the viral set points, HIV suppression trends and biomarkers of immune activation
- 3. To determine the HIV and host genetic diversity and possible transmission linkages

Infants

To characterise natural killer cell phenotype and function longitudinally from cord blood at birth up to 2 years and relate to infant HIV acquisition , morbidity and mortality

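### Section 4.10.22 names only an unadjusted relative risk for binary outcomes and does not commit to adjustment, though pregnancy outcome by non-randomised HIV status, comorbidity and HAART regimen is a primary end point

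*Protocol*

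**What the plan says.** Two sections of the protocol describe the analysis.

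- **4.10.22 Data analysis.** "Regression analysis was used to investigate the associations". The text goes straight on: "Tests of statistical significance included the 95% confidence interval of unadjusted relative risks, two-sided p values based on Chi-square" and Fisher's exact tests. No other effect measure for a binary outcome appears in the protocol.
- **4.10.21 Data Management Plan.** "Categorical data will be compared using chi squared test", and "Continuous variables will be correlated using regression models". This section mentions neither relative risks nor adjustment.

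The comparison at issue is a main one. The Protocol Summary lists among the primary end points "Pregnancy outcomes for HIV-/+ mothers with different comorbidities with or without different HAART" regimens. Objective B.2 in section 3.1 is to "Determine any association(s) between different option B+ drug regimens, adverse pregnancy outcome" and other outcomes. The key to Figure 1 (section 4.1) shows that most components are binary: preterm birth, low birth weight, birth defects, stillbirth and deaths.

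The groups are observational. Section 4.7 takes all HIV-positive women and a systematic sample of HIV-negative women, without matching. HAART regimen is recorded, not assigned.

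**The concern.** HIV status, comorbidity and regimen are not randomised, so a crude relative risk mixes their effect with that of anything else that differs between the groups and affects the outcome. The protocol names such determinants on the outcome side. Section 1.11 says: "Adverse maternal health and feotal outcomes have been shown to be more prevalent in socioeconomically-disadvantaged" women. Section 1.6 puts smoking and alcohol among the main influences on birth weight.

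If such a factor were more common among HIV-positive women, or if HIV severity differed between regimen groups, the crude relative risk would show the difference as an effect of HIV or of the regimen on a primary end point. The point is not that a covariate list is absent, since a statistical analysis plan may supply one. It is that the one measure the protocol names is the crude one, and nothing commits the study to an adjusted measure beside it.

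**Working it through.** **1. The texts side by side.**

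| Question | 4.10.21 | 4.10.22 |
|---|---|---|
| Test for binary outcomes | Chi-square | Chi-square, Fisher's exact |
| Effect measure for binary outcomes | None | Unadjusted relative risk |
| Regression | Stated for continuous variables | For associations generally; no outcome type given |
| Adjustment for confounders | Not mentioned | Not mentioned |

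Regression therefore remains possible for binary outcomes, but the only binary measure actually named is unadjusted.

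**2. Size of possible bias.** The plan has no figure to reproduce, and the documents give neither outcome risks nor confounder prevalences by group. What follows rests on assumed values.

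Take a true relative risk of 1 for HIV and one binary risk factor with relative risk R, present in a proportion p1 of HIV-positive and p0 of HIV-negative women. The crude relative risk is then

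(1 + p1(R − 1)) / (1 + p0(R − 1)).

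For p1 = 30%, p0 = 20%, R = 2 this is 1.30/1.20 = 1.083. The range is:

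| p1 vs p0 | R = 1.5 | R = 2 | R = 3 |
|---|---|---|---|
| 25% vs 20% | 1.023 | 1.042 | 1.071 |
| 30% vs 20% | 1.045 | 1.083 | 1.143 |
| 40% vs 20% | 1.091 | 1.167 | 1.286 |

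**3. False rejection.** The set-up is 600 per group (protocol), 30% vs 20%, no true effect, an assumed two-sided 5% level and 2,000 simulated studies per scenario. Rejection rates of the crude chi-square test were:

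| Risk in HIV-negative women | R = 1.5 | R = 2 | R = 3 |
|---|---|---|---|
| 10% | 6.3% | 7.7% | 12.4% |
| 20% | 7.2% | 12.0% | 23.8% |

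A normal approximation agrees: 5.8%, 7.6% and 12.6% in the first row; 6.8%, 11.0% and 22.6% in the second. For example, with a risk of 10% and R = 3, the HIV-positive risk is 10% × 1.143 = 11.43%. The difference of 1.43 points has a standard error of √((0.10 × 0.90 + 0.1143 × 0.8857)/600) = 1.785 points, so it lies 0.80 standard errors from zero. The chance of exceeding ±1.96 is then about 12.6%.

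**4. After adjustment.** Modified Poisson regression on the one simulated factor gave a mean relative risk of 1.001 to 1.004 and rejection of 4.6% to 5.4%. The standard error of the log relative risk was 0.963 to 1.006 times the crude one. Removal of the bias is built in here, because the model contains the only confounder simulated. The informative result is that precision was practically unchanged.

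**5. Population at risk.** Section 4.4 enrols at 28 to 36 weeks and preterm means before 37 weeks, so time at risk runs from 37 − 28 = 9 weeks down to 37 − 36 = 1 week. Preterm proportions therefore describe pregnancies still ongoing at enrolment. The Figure 1 key also lists spontaneous abortion as an outcome, but its stillbirth definition begins at 500 g or, if weight is missing, 22 weeks. On the gestational definition, abortion precedes the earliest entry at 28 weeks.

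**The case against.** The best reply is that 4.10.22 gives associations to regression, and objective B.2 is worded as an association. The sentence with the relative risk is a list of significance tests, introduced as a non-exhaustive one. The section is also written in the past tense, which makes it weak evidence of a fixed plan. Model family and covariates commonly belong in a statistical analysis plan, which may exist. Most of this stands. A reader might infer that the protocol declares the crude relative risk its main estimate, or rules out adjusted analysis of binary outcomes. It does neither. What remains is that the one binary measure it names is unadjusted and no sentence commits to more.

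A reader might also infer that the protocol says HIV-affected households are poorer. Section 1.11 speaks of "being born in an HIV-affected household especially of low social economic status" only when noting how little is known about that setting. This marks a subgroup of interest and is not a statement that HIV-positive women are more disadvantaged. The documents support the link from these factors to the outcome, not the link to HIV status.

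Table 5 does stratify, and some of its rows (hypertensive disorders, nutritional status) could confound a regimen contrast. But it crosses the exposures under study with each other and contains no socio-economic or behavioural factor.

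A reader might infer from the late entry that the preterm relative risk is biased. That would need gestation at entry to differ between the groups, which the documents do not show.

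Finally, prevalence and incidence by HIV status are partly descriptive aims, for which crude comparisons are legitimate. This stands too.

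**Conclusion.** The concern holds in limited form. For a primary end point that compares non-randomised groups, the protocol names an unadjusted relative risk with chi-square or Fisher tests and leaves adjustment to a general sentence on regression. An adjusted relative risk is the better main measure, and much of what it needs is already collected.

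The size is unknown. On the assumed values above, one unbalanced risk factor multiplies the crude relative risk by 1.02 to 1.29, and in the 30% vs 20% case it raises false rejection from 5% to between 6% and 24%. The lower values are small; the upper ones need a risk factor with relative risk 3. Several confounders acting in the same direction would do more, and opposing ones less. The regimen contrast was not quantified.

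**What to change.** In 4.10.21 and 4.10.22:

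- State that the main estimate for binary pregnancy outcomes is an adjusted relative risk, for example from modified Poisson or log-binomial regression. Adjust for confounders recorded at enrolment: age, socio-demographics, obstetric history and gestation at entry. Add smoking and alcohol if the questionnaire records them; section 4.8 does not name them.
- Keep the crude relative risk as secondary, and crude comparisons for descriptive prevalence and incidence.
- For regimen contrasts among HIV-positive women, consider enrolment CD4, noting that it may already reflect treatment.
- State that preterm rates apply to pregnancies ongoing at enrolment at 28 to 36 weeks, and do not count spontaneous abortion as a prospective outcome.

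The cost is the wording of two sections, a correction to the Figure 1 key and slightly more analysis work. Socio-demographics and obstetric records (4.8), dating by last menstrual period (4.4) and CD4 counts in HIV-positive mothers (4.10.11) are already planned; smoking and alcohol may need a questionnaire item. Precision was practically unchanged with one covariate; with more, intervals may widen slightly.

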4.10.23 Budget

The baseline study will cost is 120 000 US dollars and enrolment is expected to start in July 2015 and the study will continue following children up to 24 months. The current budget should be sufficient for baseline surveys. However, additional funding for the study will be sourced as the study progresses. Please note that for sub-studies the respective MPhil or PhD students will bring or source own funding for to answer their specific research questions. Activities and task are shown in **Table 6** below.

33

Table 6: Tasks and Time Frames

TASK	WHEN	who	HOW LONG	RESOURCES	COST
Get ethical approval	Y1 m1-3	PI	3 months	PI	\$700
Communication	Y1-2	Coordinator/ driver	24 months	Mobile phone hand set x 2, air time, data bundles	\$1000
Training	Y1 M1	Team	2 weeks	Teas/ lunches	\$1000
Meetings	Y1-2	Team	weekly	Teas	\$ 1000
Recruit patients	Y1 m5-8	Midwives, Coordinator	3 months	Stationery & copying	\$1000
Participant transport reimbursement	Y1-2	Research Nurse	24 months	\$5/visit x 12 visits	\$ 70 000
Transport (fuel, vehicle hire/ services)	Y1-2	Driver	24months		\$5000
Sample preparation & storage	Y1-2	Team Members	24 Months	Tubes, pipettes, boxes, accessories, PMBCs , plasma for storage	\$5000
Lab assays (local)	Y1-2	Team Members	24 Months	Kits, haematology, chemistry, urinalysis, lipid profile, T cell profiles, viral load	20 000
Data entry,	Y1-2	Biostatistician	24 Months	Laptops x 3, dongle, memory sticks.	\$ 2500
Allowance	Y 1 M 1-6	PI	6 months	Research nurses, driver, secretary , coordinator and lab scientist, data clerks	\$15 000
Conferences	Y2	PI/co-investigators		Travel and subsistence, tickets	\$5 000
Publications	Y2	Team Members		Publication fees	\$ 2000

Y: Year

4.10.24 Research Outcomes

- Characterisation of comorbidities of HIV negative and HIV positive mothers
- Immune activation profiles for different comorbidities
- HIV vertical transmission rate in the era of option B+ among mothers with chronic HIV infection
- HIV incidence and postpartum vertical transmission among mother with acute HIV infection
- Transmission linkages of acute HIV infection

Research outcomes will entail improved knowledge of HEU infants immunological abnormalities and genetics resulting in their better clinical management. There will also be technology transfer in

molecular biology and genetics techniques through the establishment of research networks both locally and internationally. The project will generate a critical mass of local professions with diverse expertise as they attain higher degrees, MPhils and PhDs from sub-studies. At least ten (10) papers will be published from the parent study material.

